8.3 Sample Size and Power Determination

To calculate power, we started from an ambitious but realistic estimate of the population available at the participating recruitment sites. We intend to recruit 62 subjects, although 25 subjects will be adequate to detect a difference between real and sham stimulation within each group (alpha = 0.05; power = 0.8). Although our historical attrition rate has been 15%, we will conservatively anticipate a 25% attrition rate and will therefore enroll 31 subjects in each PPA variant arm.

CONFIDENTIAL

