8.4.2 Identifying Predictors of Treatment response

We will employ a binary outcome (responder vs. non-responder), based on a change in WAB-AQ of 5 points, which has been recognized as clinically meaningful change in aphasia severity (Elman et al., 1999). We will pursue a series of univariate logistic regression analyses interrogating the following variables, in order to determine which are likely predictors of response to tDCS: PPA variant (naPPA/lvPPA, svPPA, extent of brain atrophy (cortical thickness in the designated language network regions), hub scores, and baseline symptom severity (baseline WAB-AQ). Akaike information criterion (AIC) will be used to develop and select a final model that includes the predictors of tDCS response previously identified as relevant in the univariate analyses. First, the full model containing all relevant predictors will be compared against models with one of each of the predictors removed, to evaluate the extent to which predictors may be correlated or may uniquely contribute to the model despite some potentially shared contribution. The final model will contain age, duration of disease, and sex as covariates and only those predictors identified as unique contributors to tDCS response by the AIC selection procedure.

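### Section 8.4.2 selects predictors of tDCS response by an undefined univariate screen and AIC deletion, without correction or validation; under the null a noise predictor survives in roughly 20% to 80% of trials, depending on choices the plan leaves open

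*Combined protocol and SAP*

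**What the plan says.** Section 8.4.2 classifies participants as responders or non-responders by a 5-point WAB-AQ change. It then proceeds in three steps.

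1. Univariate screening: "We will pursue a series of univariate logistic regression analyses interrogating the following variables". The variables are PPA variant, regional cortical thickness in the language network, hub scores and baseline WAB-AQ. Those judged relevant go forward; what counts as relevant is not defined.
2. AIC: the full model is compared with models that each omit one predictor.
3. Final model: age, disease duration and sex, plus "only those predictors identified as unique contributors to tDCS response by the AIC selection procedure".

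Section 8.3 fixes the sample: "We intend to recruit 62 subjects", and "we will conservatively anticipate a 25% attrition rate and will therefore enroll 31 subjects in each PPA variant arm".

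Section 8.4.2 gives no screening threshold, count of thickness or hub variables, expected responder rate, multiplicity control, shrinkage or validation. The FDR threshold, leave-one-out validation and permutation tests in section 8.4.3 belong to other analyses: the node-loss regression, the support vector models and the localisation test.

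**The concern.** Screening, deleting and reporting on one data set yields survivors that look stronger than they are. AIC does not repair this. For a one-parameter term it is a lenient test, and here it acts on variables already picked because they looked relevant. Calling the survivors unique contributors presents a selection result as a finding.

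The covariates add a second problem. Age, duration and sex are named only for the final model, so the text allows a thickness or hub variable to be selected before adjustment, even if its association with response only reflects age or disease duration.

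At stake is what the trial may say about who responds to tDCS, which is one of the secondary objectives in section 2.2. The comparison of real with sham stimulation is not affected.

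**Working it through.** **Sample available.** Section 8.4.2 states no figure of its own, so the starting point is section 8.3. Its 31 per group follows from 25 × 1.25 = 31.25. Dividing by retention would give 25 / 0.75 = 33.3, so 34; that is a separate matter. What counts here is the expected number of completers: 62 × 0.75 = 46.5, taken as 46. At the historical 15% attrition it is 62 × 0.85 = 52.7. Everyone receives real stimulation in one period (section 3.1.5), so I assume one responder classification per completer.

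**AIC as a test.** AIC keeps a 1-df term when its likelihood-ratio chi-square exceeds 2, and P(chi-square, 1 df > 2) = 0.157.

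**Closed form.** For K independent noise candidates and one per-term threshold a, P(at least one passes) = 1 − (1 − a)^K.
- K = 4: 1 − 0.95^4 = 18.5% at 0.05; 1 − 0.843^4 = 49.6% at 0.157.
- K = 10: 1 − 0.95^10 = 40.1% at 0.05; 1 − 0.843^10 = 81.9% at 0.157.
- For comparison, four prespecified tests at 0.05/4 give 1 − 0.9875^4 = 4.9%.

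**Simulation of the whole procedure under a complete null.** Settings: n = 46; one binary and K − 1 continuous candidates, independent or correlated at 0.4; 9 or 14 responders; univariate likelihood-ratio screen, then drop-one AIC, with and without three noise covariates. The table shows how often at least one noise predictor was retained.

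| Candidates (assumed) | Screen p<0.05 | p<0.10 | 0.157 to 0.20 | No screen |
|---|---|---|---|---|
| 4 | 18-21% | 31-38% | 39-53% | 52-61% |
| 8 | 29-38% | 43-62% | 51-77% | 81-87% |
| 12 | 38-51% | 52-75% | not run | not run |
| 20 | 46-69% | 56-90% | not run | not run |

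Simulations with 10 candidates gave 39-43% at p<0.05 and 78-82% at 0.157 to 0.20.

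**Does the responder count drive this?** No. With four independent candidates and p<0.05, the rate is 21%, 20% and 21% with 9, 14 and 23 responders.

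**What few responders do.** The documents give no responder rate. If 20-30% respond, 46 × 0.20 = 9.2 and 46 × 0.30 = 13.8, so 9 to 14 responders. Four predictors and three covariates make seven terms: 9/7 = 1.3 to 14/7 = 2.0 events per parameter. With one predictor retained, 9/4 = 2.3 to 14/4 = 3.5. At 15% attrition, 52.7 × 0.20 = 10.5 and 52.7 × 0.30 = 15.8, so 1.5 to 2.3 for seven terms. The most favourable rate for 46 completers is 50%, which gives 23/7 = 3.3; above 50%, non-responders become the smaller class.

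**The case against.** Several objections stand, and they limit the point.

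- **A reader might infer that the plan will usually name a false predictor.** The documents do not support that. Section 8.3 works at "alpha = 0.05; power = 0.8" and section 8.4.3 uses an FDR threshold of 0.05, so 0.05 is a natural guess for the unstated screen. With four candidates the false-selection rate is then about 20%. It passes one half only with a looser screen or roughly 12 to 14 or more independent candidates at 0.05, and the plan specifies neither. After a 0.05 screen, the AIC step adds almost nothing (about 20% against 18.5%).
- **A reader might infer that a small number of responders causes the false selection.** It does not; the candidate count and the thresholds do. Nor is 9 to 14 a figure from the plan.
- **Overfitting is not all due to selection.** Selected noise models showed a mean apparent AUC of 0.74-0.81. A fixed, unpenalised seven-variable noise model gave 0.73-0.77, and three noise covariates alone gave 0.64-0.67. Much of the optimism comes from the small sample, and the plan names no AUC. This argues for shrinkage and correction as well as for dropping the screen.
- **Covariate order is permitted, not stated.** The text does not say whether the AIC comparisons omit age, duration and sex.
- **Importance.** The Study Summary places identifying responders under its primary objective, but section 2.1 makes efficacy primary and section 2.2 lists prediction of response as secondary. Section 8.4.1 calls baseline severity as a predictor exploratory. The analysis should not be treated as the trial's primary one.

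Against this, four candidates is close to the minimum: section 8.4.2 refers to regions and hub scores in the plural, and section 8.4.3 works node by node. Section 8.4.2 carries no exploratory label. No scenario tried came near 5%.

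**Conclusion.** The point holds as a should-fix weakness in a secondary analysis. The procedure is data-driven at two stages, has an undefined threshold and candidate list, and is uncorrected. With no true predictor and 46 completers, it names at least one contributor in roughly 20% of trials (4 candidates, p<0.05) to about 80% (10 candidates, 0.157 to 0.20). The candidate counts, thresholds and correlations are assumptions, because the plan gives none of them. The width of that range is itself part of the problem: the error rate would be settled by choices made after the data are seen.

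Separately, the final model would rest on few events per parameter: 1.3 to 2.0 with seven terms if 20-30% respond, and at most 3.3 at any responder rate with 46 completers. Its coefficients and apparent performance would be unstable and too favourable. The null simulations used noise covariates, so they do not measure the risk from selecting before adjustment; that part rests on the wording alone.

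**What to change.** Amend section 8.4.2 as follows.

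1. Drop the univariate screen.
2. Prespecify a small, fixed candidate set covering the four named domains. Choose the regional thickness and hub summaries in advance to match the variant-specific hypotheses. A single mean hub score over the whole language network may not suit, because section 1.1.4 expects different language centres to be affected in different variants, with hub scores rising early and falling later.
3. Fit these candidates with age, disease duration and sex in one penalised logistic model, and name one method, for example ridge. Ridge and Firth should not be offered as alternatives: Firth mainly corrects bias and shrinks only mildly.
4. If selection is kept, state the threshold and the full candidate list, and include the three covariates at every step.
5. In either case, report bootstrap optimism-corrected performance, with every resample repeating the whole procedure, including any screening and selection.
6. Label the analysis exploratory and stop describing surviving variables as unique contributors.

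This is a cheap improvement. It changes analysis text and needs a little more programming; no visit, sample size or treatment is touched. The downside is less region-level detail and reported performance that will look less favourable.

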8.4.3 Network Neuroscience measures of response to tDCS + CILT

We will first test for the hypothesized relationship between node loss and hub scores by expressing node loss as a quadratic term in a multiple regression using the gray matter thinning at each node in the language network to predict hub scores, covarying for subject age and disease onset, with an FDR-corrected threshold of 0.05. Then, we will use a data-driven machine learning approach—support vector regression—using multivariate hub scores (Fornito et al., 2015) throughout the brain to predict behavior. We will use a leave-one-out cross validation strategy to identify the combination of nonlinearly weighted variables that predict behavior. The value of the machine learning model will be evaluated in terms of percentage of variance explained relative to selecting a similarly sized set of random variables (neuroimaging features including region cortical thickness and individual white matter connections) in 10,000 permutations for both the traditional regression and support vector regression models. It will additionally be tested against network density—the total connectivity of the network—as a control condition. Then, to test whether strong hubs account for the greatest variance in the data, we will correlate the support vector regression weights with region hub scores post-hoc. A significant positive correlation would indicate that stronger hubs account for higher variance in behavioral scores.

We will then use multiple regression to assess stimulation condition as a predictive variable for each language network node. If the predictor illustrates that hub scores increase in the presence of active tDCS, we will test whether effects tend to be concentrated near the site of

CONFIDENTIAL

stimulation using a permutation test in which we shuffle the assignment of significant nodes for each network statistic uniformly at random across the brain. If the number of nodes concentrated in the anterior perisylvian nodes encompassed by our area of stimulation is greater than 95% of permutations, it will establish that the effects of mCILT or tDCS + mCILT are local to this region. Moreover, it will allow us to examine whether the effects of stimulation on hub scores are observed in different PPA phenotypes that express pathology at the site of stimulation (as in our nPPA/lvPPA subject) or remote from the site of stimulation (as in our svPPA subjects). Finally, to test if patterns of hub scores across the brain distinguish pre-from post-treatment, we will train support-vector classifiers in a leave-one-out fashion to distinguish pre-and post-treatment conditions within each phenotype using all node hub scores. We will use permutation testing to examine the accuracy of the classifiers against 10,000 null permutations to examine the significance of our results. Further exploratory analyses will examine the specific effect of mCILT alone on language network properties.

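### Correlating SVR weights with hub scores cannot show that stronger hubs explain more variance, and the SVR benchmark is open to selection optimism unless the plan rules out or nests all selection and tuning

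*Combined protocol and SAP*

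**What the plan says.** Section 8.4.3 of the combined protocol and SAP applies SVR to hub scores "throughout the brain to predict behavior". On model building it says: "We will use a leave-one-out cross validation strategy to identify the combination of nonlinearly weighted variables that predict behavior". On evaluation it says: "The value of the machine learning model will be evaluated in terms of percentage of variance explained", the comparison being made "relative to selecting a similarly sized set of random variables (neuroimaging features including region cortical thickness and individual white matter connections) in 10,000 permutations". A further control is named: "It will additionally be tested against network density". Then, to ask whether strong hubs matter most, "we will correlate the support vector regression weights with region hub scores post-hoc"; a significant positive correlation is to be taken as showing that stronger hubs account for more of the variance in behaviour.

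The section does not state the kernel, the number of nodes, any tuning rule or whether predictors may be dropped. Nor does it say whether variance explained is in-sample or out-of-sample, or whether weights are taken in absolute value. For the separate classifiers of pre- versus post-treatment scans, the same section says that every node enters and that accuracy is tested against a permutation null. It says neither for the SVR.

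**The concern.** Two steps of the inference are exposed.

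The first is the reading of the weights. The model is described as nonlinearly weighted, yet the test needs one weight per region. Even where such weights exist, the direction of a region's effect is not how much it explains. The planned correlation could support the hub hypothesis when it is false and miss it when it is true.

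The second is the benchmark. If leave-one-out is used both to choose the predictors (or settings) and to score them, the score is optimistic. The random sets, drawn "relative to selecting a similarly sized set of random variables", are not described as going through the same choice. A hub model with no true signal could then look better than other imaging features.

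At stake is what may be concluded under the secondary objectives in section 2.2 that relate hub characteristics to aphasia severity and connectivity to response.

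**Working it through.** The plan gives no expected variance explained, error rate or threshold for the SVR, so it has no figure to reproduce. The two parts are checked separately.

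**Part 1: weights and variance explained**

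- Linear SVR: f(x) = b + Σⱼ wⱼxⱼ, with j running over regions. For uncorrelated hub scores, Var(f) = Σⱼ wⱼ² Var(xⱼ). Region j contributes wⱼ² Var(xⱼ), so the sign of wⱼ drops out.
- Equal importance can give a positive correlation: if strong hubs have weight +c and weak hubs −c, with equal variances, every region contributes c² Var(x), yet weights rise with hub strength.
- Greater importance can give a negative one: if wⱼ = −c·hⱼ, with hⱼ the hub strength and c positive, the contribution rises with hⱼ², yet the correlation is −1.
- Nonlinear kernel: f(x) = b + Σᵢ aᵢK(xᵢ, x), with i running over participants. The coefficients belong to participants, not regions. A fitted RBF-kernel SVR duly returned no per-region weights.

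Simulation of the linear case, all settings assumed: 50 participants, 40 regions with hub strength evenly spaced from 0 to 1, noise SD half the signal SD, C = 1, 200 data sets; r > 0.312 counts as significantly positive.

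| Truth | Mean r, signed weights | Mean r, squared weights | Significantly positive (signed) |
|---|---|---|---|
| Importance rises with hub strength, random signs | 0.01 | 0.38 | 4% |
| Equal importance; strong hubs +, weak hubs − | 0.62 | −0.02 | 99% |
| Importance rises with hub strength, all negative | −0.46 | 0.34 | 0% |

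**Part 2: the benchmark when there is no signal**

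Score: leave-one-out variance explained = 1 − Σ(yᵢ − ŷ₍₋ᵢ₎)² / Σ(yᵢ − ȳ₍₋ᵢ₎)². A pass means exceeding the 95th percentile of the random feature sets. That cut-off is my assumption.

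RBF-kernel SVR, pure noise. Assumed: 50 participants, 100 hub nodes, 300 other features, sets of 10, C = 1, epsilon = 0.1, 40 random sets per data set, 88 data sets. The median benchmark 95th percentile was 0.07.

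| How the 10 hub scores are obtained | Median variance explained | Pass |
|---|---|---|
| Chosen by correlation on all data, then scored | 0.21 | 84/88 (95%) |
| Best of 50 candidate sets by leave-one-out, same value reported | 0.14 | 80/88 (91%) |
| Chosen afresh inside each training fold | −0.19 | 11/88 (12.5%) |
| Fixed in advance | −0.13 | 4/88 (4.5%) |

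Kernel ridge as a fast stand-in (25, 50 and 62 participants; 50, 100 and 200 nodes; 100 data sets per setting) gave 75% to 100%, 76% to 90% and 2% to 13% for the first, second and fourth rows. Of these sizes, 62 and 25 come from section 8.3; node counts are assumed.

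Sensitivity to the benchmark: ridge regression, forward choice of 5 of 100 hub scores by leave-one-out, 46 participants (62 × 0.75 = 46.5).

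- With 400 pure-noise benchmark features, noise hub scores passed in 60 of 60 data sets (mean leave-one-out R² 0.39), and in 40 of 40 on a repeat.
- When each benchmark feature correlated 0.2, 0.3 or 0.4 with behaviour, they passed in 36, 17 and 0 of 40.
- With hub scores also correlated among themselves (five factors), they passed in 25, 1 and 0 of 40.
- With all hub scores entered and none selected, they passed in at most 2 of 40 in every setting.

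Check of the remedy: with the behavioural score shuffled 100 times and selection repeated each time, noise passed in 3% to 11% across the nine kernel-ridge settings, mean 7%. With 100 shuffles the cut-off's own expected level is about 6/101 = 5.9%. Likewise, 40 random sets give about 3/41 = 7.3%, or 88 × 3/41 = 6.4 expected passes against the 11 seen with nesting. Nesting therefore removes most of the inflation, but these runs do not show that it restores the nominal rate.

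**The case against.** The best reply concerns the second part. The hub scores are described as covering the brain; no selection algorithm, subset size or stopping rule appears; and the sister classifier analysis uses every node. Identifying the combination may only mean estimating how all the scores are weighted, and a similarly sized random set may mean as many features as there are hub scores. On that reading there is no inflation. This stands, so the benchmark point is conditional.

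A reader might infer from the high pass rates that noise would almost always beat the planned benchmark. The documents do not support this. They state neither selection nor a 5% threshold for the SVR; the 95% rule in section 8.4.3 belongs to the test of where significant nodes lie. Section 1.1.1 ties language deficits to regional atrophy, so cortical thickness may well carry signal, and the pass rate then fell as low as zero. Those correlations are also assumed, and the benchmark errors were independent, which favours the benchmark.

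A reader might also infer that a secondary objective could be declared met on noise. No such decision rule is given, and prediction of response has its own analysis in section 8.4.2. Nor is the random-feature comparison misconceived: with network density, it asks whether hub scores do better than other features, which is a fair question of specificity.

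On the weights, it may be said that the text does not exclude absolute values and labels the step post-hoc. Absolute or squared weights would answer the sign problem for a linear kernel on standardised scores. They would not supply regional weights for a nonlinear one, and the plan states neither.

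**Conclusion.** The weights rule is wrong as written, whether or not predictors are selected. It is undefined for a nonlinear-kernel SVR. For a linear one, it can be positive when strong hubs are no more important (99% in the example) and negative when they are (mean r −0.46, never significantly positive). The algebra assumes uncorrelated hub scores; the percentages are illustrative.

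The benchmark point holds only if something is selected or tuned without an outer loop, which the present wording permits but does not establish. In that case variance explained is optimistic and noise can pass. The rate cannot be fixed from the documents: node count, set size, kernel, tuning and signal in the benchmark features are all missing, and the simulated range runs from 0 of 40 to 60 of 60. The network-density control does not remove this optimism, since it involves no selection either.

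This is a secondary analysis. The primary WAB-AQ analysis in section 8.4.1 is untouched.

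**What to change.** 1. State the kernel, and replace the weight correlation by a sign-free importance for each region: the loss of out-of-sample variance explained when that region's hub score is permuted. With leave-one-out, give each held-out participant another participant's value for that region, predict from that fold's model, and recompute the pooled figure. Relate this importance to hub strength, and note that importance is shared among correlated regions.
2. Say which model is meant: either all hub scores enter with settings fixed in advance, or all selection and tuning is done inside each training fold, with the random feature sets put through the same steps.
3. In both cases report only variance explained for participants left out of every choosing and fitting step.
4. Take the p-value from permuting the behavioural score across participants, repeating the whole pipeline for each shuffle.
5. Keep the random-feature and network-density comparisons, labelled as tests of specificity.

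The cost is SAP wording and computing time, since each shuffle repeats every fold. The reported variance explained may be lower. No data collection changes.

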1.1 Background and Relevant Research

1.1.1 Neurodegeneration in PPA variants

Specific language deficits that emerge in persons with different PPA variants relate to the regions of the left hemisphere language networks that are selectively affected by neurodegeneration (Grossman, 2010). Atrophy is observed in the left inferior frontal lobe and insula in persons with naPPA. Individuals with lvPPA show atrophy of the left posterior temporal and parietal lobes. Semantic variant PPA (svPPA) involves atrophy of the anterior and ventral temporal lobe (Grossman, 2012; 2018; Agosta et al., 2013; Giannini et al., 2017). Thus, each PPA syndrome affects a portion of the neural network supporting language, while other portions of the language network remain relatively preserved. Unfortunately, while our expanding understanding of the anatomic, neural, and functional properties of language networks has enabled greater insight into the neural changes that underlie PPA symptoms, there are no approved therapies that leverage this knowledge in order to advance targeted treatments for neurodegenerative aphasias.

1.1.2 tDCS to treat PPA

Transcranial direct current stimulation (tDCS), a noninvasive brain stimulation technique, is a promising intervention in aphasia. TDCS delivers low-intensity electrical current to the brain through electrodes placed on the scalp. This low-intensity current can produce small shifts in the resting membrane potential of large numbers of neurons which is believed to alter neuronal firing rates and thus modulates patterns of brain activity (Bindman et al., 1964; Stagg & Nitsche, 2011; Rahman et al., 2013). Evidence indicates that repeated stimulation with tDCS can result in lasting changes in cognitive performance (e.g. Ries et al., 2009; Flöel et al., 2012). A number

CONFIDENTIAL

of studies indicate that tDCS may serve as an effective intervention for aphasia (Reviewed in Norise & Hamilton, 2017). In our own prior work, we found that 10 days of tDCS in subjects with post-stroke aphasia resulted in a ~17% improvement in aphasia severity, compared to sham tDCS. This improvement was measured two months after discontinuation of stimulation (Shah-Basak et al., 2016).

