1.1.4 Using brain networks to predict tDCS response

Evidence points toward the importance of brain network hubs—nodes that are connected to many other nodes by edges—in neurodegenerative disorders. Nodes with high hub centrality are critical participants in a wide range of network operations supporting cognitive functions (van den Heuvel & Sporns, 2013) and are disproportionately affected in neurological syndromes (Stam, 2014). The tendency for a node to be a hub can be distinguished from more general measures such as network density, the total number of connections in a network, and can be expressed as a hub score, which quantifies the centrality of a node in information processing in a network (van den Heuvel, 2010). Brain regions with especially high hub scores participate in many processing pathways within the brain. Across the spectrum of neurodegenerative disorders, it is suspected that as nodes in critical brain areas are progressively degraded by disease, this is associated with changes in the recruitment of remaining hub nodes (Stam, 2014). Early in the course of degenerative disease, as specific brain regions are selectively affected, it is believed that there is an *increase* in the connectivity of remaining hubs in those regions that partially compensates for lost nodes and helps to maintain performance (Stam, 2014). However, as worsening disease leads to greater node loss, these compensatory changes cannot keep pace with neurodegenerative deterioration, resulting in decreasing hub scores in affected regions (Buckner et al., 2009; Engels et al., 2015). Eventually, when degenerated regions are severely affected, hub scores decline dramatically as the few remaining nodes do not harbor sufficient connections to contribute to networks. In the case of PPA, residual language abilities would then depend on the activity of relatively spared language regions. In a preliminary analysis of 65 subjects with PPA we found that hub scores are indeed decreased in different language centers in PPA variants. Thus, the hub score could serve as a metric in PPA to describe how affected and spared regions impact network functions at different stages of disease. Brain network hubs could also be positively influenced by interventions that enhance their connectivity. We posit that changes in hub scores could also provide a framework for understanding the impact of tDCS on language networks in persons with PPA.

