2.2 Secondary Objectives

- Utilized network analyses to directly interrogate the roles of structural and function connectively in the language network in PPA.
 - Determine whether baseline hub characteristics of the language systems of persons with naPPA/lvPPA, and svPPA influence aphasia severity.
 - Determine whether tDCS induced behavioral effects induce changes in the language network properties.
 - Determine whether structural and functional connectivity features can predict responsiveness to tDCS.

3 Investigational Plan

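### The hub-score model of behavior in 8.4.3 has no PPA variant benchmark, so it could credit hubs with variance that variant membership alone explains

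*Combined protocol and SAP*

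**What the plan says.** Section 8.4.3 uses hub scores "throughout the brain to predict behavior" by support vector regression. Leave-one-out cross-validation is meant to "identify the combination of nonlinearly weighted variables that predict behavior". No covariate, variant term or stratification is listed for this model. The result is judged by the percentage of variance explained, against two comparators: similarly sized sets of random imaging features (10,000 draws, including regional cortical thickness and white matter connections) and network density, a single measure of total connectivity.

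The regression that precedes it, from gray matter thinning to hub scores, is run "covarying for subject age and disease onset", again without variant. Variant is handled elsewhere:

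- Section 8.4.1 estimates the treatment effect for each variant group.
- Section 8.4.2 makes variant a candidate predictor of response.
- The pre/post classifiers later in 8.4.3 are trained "within each phenotype using all node hub scores".

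On the link between hubs and variant, section 1.1.4 reports from a preliminary analysis of 65 subjects that "we found that hub scores are indeed decreased in different language centers in PPA variants". Section 1.1.1 says that "each PPA syndrome affects a portion of the neural network supporting language". The question that the model serves is the first sub-bullet of section 2.2: "Determine whether baseline hub characteristics of the language systems of persons with naPPA/lvPPA, and svPPA influence aphasia severity".

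**The concern.** A whole-brain hub pattern that differs by variant can serve as a label for variant. If the two halves of the sample also differ in mean behavior, a model that does no more than recognize the variant will predict behavior. Leave-one-out validation does not prevent this, because the held-out participant's variant is just as recognizable as everyone else's.

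The stake is interpretation. A pooled result could be reported as hub properties relating to severity among persons with PPA, when it shows only that the two groups differ in both hubs and severity. The next step in 8.4.3 correlates the model weights with hub scores and reads a positive correlation as stronger hubs accounting for more variance in behavior. Any variance credited in error would carry into that mechanistic conclusion.

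**Working it through.** The plan states no numerical figure for this model, so there is nothing to reproduce.

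**Inputs from the documents.** 31 naPPA/lvPPA and 31 svPPA participants (section 4.5); hub scores that differ by variant, with no size given (1.1.4); two comparators, random feature sets and density (8.4.3).

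**Assumptions.** The gap in mean behavior between the two groups, d, in within-group SDs, is not given; the range taken is 0 to 1.2. The size of the hub shift between variants and the number of nodes are not given either. The plan sets no threshold for beating the random feature sets, so a pass is taken as p ≤ 0.05.

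**Step 1: what variant alone can explain.** With two equal groups and within-group variance 1, the between-group variance is d²/4, so R² = (d²/4)/(1 + d²/4).

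- d = 0: 0
- d = 0.5: 0.0625/1.0625 = 0.059
- d = 0.8: 0.16/1.16 = 0.138
- d = 1.0: 0.25/1.25 = 0.200
- d = 1.2: 0.36/1.36 = 0.265

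These are ceilings. A hub model reaches them only if it identifies variant perfectly.

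**Step 2: does the planned random-feature comparison remove it?** Two simulations used 62 participants and 100 nodes. Hubs and behavior both depended on variant, and there was no hub-behavior link within variant. Every pass is therefore spurious.

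*First simulation* (linear-kernel least squares as a stand-in for support vector regression; 20-40% of nodes shifted by 0.8 SD; 150 runs, 100 random sets each):

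- hubs carry more variant information than the pool: 7-8% at d = 0.5, 11-17% at d = 0.8, 11-37% at d = 1.2
- equal information: 5-7%

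*Second simulation* (Gaussian-kernel ridge regression as the stand-in; about 40% of hub nodes shifted; pool of 600 features; 200 runs, 99 random sets each), at d = 1.0:

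- hub shift 1.0 SD; about 10% of pool features shifted by 0.5 SD: 59.5%
- hub shift 1.0 SD; about 40% of pool features shifted by 0.5 SD: 36%
- hub shift 1.0 SD; about 40% of pool features shifted by 1.0 SD (equal): 7.5%
- hub shift 0.5 SD; about 40% of pool features shifted by 1.0 SD (hubs carry less): 1.5%

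With d = 0 in the first of these four settings, the rate was 8.5%. The comparison is therefore not an exact 5% test even without a gap, and 59.5% should be read against 8.5%. The Monte Carlo standard error with 200 runs is √(0.05 × 0.95/200) = 1.5 points near 5%, and √(0.36 × 0.64/200) = 3.4 points near 36%.

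**Step 3: does density remove it?** In the second simulation, density was taken as the mean of the node scores. Hub R² exceeded density R² in 84.5-93.5% of runs at d = 1.0, against 48% at d = 0. One global number cannot absorb decreases that sit in different regions in different variants.

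**The case against.** The strongest reply is that the plan already has a suitable control. The random feature pool includes regional cortical thickness, and section 1.1.1 describes the variants by where atrophy occurs, so the pool should carry variant information too. The documents never show that hubs carry more. Where they carry the same or less, spurious passes are about 5-7.5% or lower. This stands, and it makes the comparison a partial safeguard. It is not a full one, because the documents do not show the reverse either, and the pool also contains individual white matter connections whose variant information is unknown.

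A second reply is that no behavioral gap is documented, and that 8.4.3 says only behavior; severity comes from section 2.2. Both are true. With no gap there is nothing for variant to explain.

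A reader might infer stronger things. One is a much higher false-positive rate, from shuffling behavior across all participants. That does not describe the planned test: 8.4.3 plans no such shuffle for this model, and the label permutation it plans for the classifiers already sits within phenotype. Another is that variant must be added to the thinning-to-hub regression, or its means removed from the hub scores. The documents do not support requiring this. Variant-specific atrophy is part of the pathway that section 1.1.4 hypothesizes, and the thinning regression has no behavioral outcome.

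**Conclusion.** The gap in the plan is real and limited. As written, the model can credit hub scores with between-variant variance: nothing at a zero gap, and up to about 6%, 14% and 26% at assumed gaps of 0.5, 0.8 and 1.2 SD. Whether the random-feature comparison would catch this depends on whether hubs or the random features separate the variants better, which the documents leave open. If hubs do, spurious passes were 7-37% across gaps of 0.5-1.2 SD in one simulation and 36-60% at 1.0 SD in the other.

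These rates rest on assumed gaps, hub shifts and node counts, a two-group variant structure, stand-in models and an assumed 5% threshold. Pooling over variants is read from the absence of any variant term, in contrast with the classifiers that are explicitly within phenotype.

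A reader might infer that any hub-behavior result from this trial would be an artifact. The documents do not support that, since neither a behavioral gap nor an advantage of hubs in separating variants is shown. The point concerns one step of a secondary objective and leaves the primary endpoint and the treatment model untouched. It is a cheap improvement.

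**What to change.** In 8.4.3, beside random features and density, add a variant-only model as a third benchmark. It uses naPPA/lvPPA versus svPPA, the groups in section 4.5, under the same leave-one-out scheme. Report the variance that hub scores explain beyond it, that is, variant plus hub scores compared with variant alone, alongside the pooled result. Claim that hubs relate to severity within persons with PPA (first sub-bullet of 2.2) only if that increment is supported. If behavior is shuffled to obtain a p-value, shuffle within variant group; in the simulations this held the false-positive rate at 3-7%.

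Do not require variant in the thinning-to-hub regression. At most, report that regression with and without variant as a sensitivity analysis.

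The cost is a few lines of plan text and a little more analysis; the variant group is already needed for the counterbalancing in section 3.1. The downside is that purely between-variant differences no longer count as evidence of a within-variant hub effect, although the pooled result still shows them. A two-level benchmark may leave some difference between naPPA and lvPPA unremoved, since the plan sets numbers only for the combined group.
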